21 APPENDIX C: BIOMARKER SUBSTUDY

Type 2 diabetes (DM) and prediabetes exacerbate the complications of all forms of cardiovascular disease, and particularly heart failure.^{1, 2} DM can directly affect the myocardium, leading to increased left ventricular (LV) hypertrophy, altered LV remodeling, and reduced systolic and diastolic function.³ In the presence of hypertension or ischemia/infarction, DM worsens adverse LV remodeling and dysfunction, which results in worse heart failure (HF) symptoms and increased mortality.⁴⁻⁶

The recently released EMPA-REG OUTCOME trial noted a 38% relative risk reduction of cardiovascular death with empagliflozin, a SGLT-2 inhibitor, versus placebo in patients with diabetes and established CVD.⁷ Though the trial was predominantly of diabetic patients with coronary artery disease, the majority of the benefit appeared to be due to the reduction in hospitalizations for heart failure (a 35% relative risk reduction), and prevention of heart failure related and arrhythmia-related deaths. The mechanism of action for such a dramatic benefit in prevention of HF and cardiovascular mortality is not well understood, but does not appear to be due to the glucose lowering effects of empagliflozin.

It is therefore likely that mechanisms beyond glucose lowering and diuresis are behind the reduction in HF events and CV mortality with SGLT-2 inhibitors.⁸ We hypothesize that the majority of the benefit of SGLT-2 inhibitors in HF is due to a reduction in oxidative stress, (thus improving both systolic and diastolic function), improvement in endothelial function (thus decreasing vessel stiffness) and possible neurohormonal and anti-inflammatory effects. Supporting this hypothesis are rat models where SGLT-2 inhibition was shown to normalize endothelial function, reduce oxidative stress in aortic vessels, reverse a pro-inflammatory phenotype, and improve AGE/RAGE signaling all pathways of potential importance to a reduction in arterial stiffness.⁹

The biomarker substudy will address the following Specific Aims:

1. Specific Aim #1: To assess the impact of dapagliflozin vs. placebo on known markers of myocardial fibrosis/necrosis, inflammation, and oxidative stress in patients with chronic HF with reduced systolic function (with and without diabetes)

We will measure systemic biomarkers of oxidative stress: Uric Acid, Fibrosis: galectin-3 (Gal3), ST-2, myocyte necrosis: High sensitivity cardiac troponin T (hs-cTnT), and inflammation: high-sensitivity C reactive protein (hsCRP), interleukin-6 (II-6). (See Appendix C Biomarker Summary Table). The change in biomarkers between 0, 6 and 12 weeks will be compared between dapagliflozin and placebo.

Anticipated results: We hypothesize that multiple biomarkers reflecting diverse biological pathways would be significantly decreased in patients receiving dapagliflozin vs. placebo. Our overarching hypothesis is that patients taking dapagliflozin for 12 weeks will have a significantly greater reduction in biomarkers of oxidative stress (one of the most likely underlying mechanisms of benefit of SGLT-2 inhibitors) than those on placebo.

 Specific Aim #2: Examine the relationship between biomarkers of myocardial fibrosis/necrosis, inflammation, and oxidative stress and clinical outcomes, including heart failure specific biomarkers (BNP, NTproBNP), as well as patients' symptoms and functional status (KCCQ and 6-minute walk test) Linear regression will be employed with heart failure specific biomarkers (BNP, NTproBNP). KCCQ and 6 minute walk, as dependent variables (separate models); independent variables will include biomarkers of oxidative stress, fibrosis/necrosis, inflammation and other potential confounders; the biomarkers will be included in separate models and chosen based on the strongest univariable relationships between biomarkers and the clinical outcomes.

Anticipated results: We hypothesize that those patients with the greatest clinical benefit (by BNP, NTproBNP, KCCQ or 6 min walk) will be those with a significant reduction in pro inflammatory, fibrotic, and oxidative stress biomarkers.

3. Specific Aim #3: Preserve residual blood specimens (banked biospecimens) for long-term storage so that evaluations for additional biomarkers or genetic analyses could be performed in the future.

To protect subjects' confidentiality, the banked biospecimens and data generated from them will be coded with the subject's study ID number. Samples will be kept in a secure storage area. Data will be stored on password-protected computer systems. The key between the code and the subject's personal identifiers will be held at the study site; the researchers using the biospecimens and data generated from them will not have access to the key nor any personally identifying information.

It is very unlikely that results generated from the banked biospecimens will have any clinical, diagnostic, or therapeutic implications for the individual study participants. Subjects are notified in the informed consent document that their results will not be given to them, to family members or other physicians; nor will they be recorded in the subject's medical record.

A research proposal would be submitted to the **second second** IRB for approval of any future analysis that might be conducted on the banked biospecimens.

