2.5 Multiple Testing

Both primary hypotheses will be tested at the 2-sided 5% significance level. In the case of non-significant findings for the first dual primary endpoint, the second dual primary endpoint will be tested at the 2-sided 5% significance level but will be regarded as an exploratory endpoint, and a nominal P value will be produced. No adjustments for multiplicity will be made for secondary and exploratory endpoints.

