The association between the change in lung fluid volume from baseline to 6 and 12 weeks and clinical outcomes, including heart failure specific biomarkers (BNP, NT pro-BNP), as well as patients' symptoms and functional status (KCCQ overall summary score and 6-minute walk test), will be examined using generalized mixed linear models with clinical outcomes as dependent variables (separate models) and the change of lung fluid volume at 6 and 12 weeks as independent variables. Other potential confounders are age, eGFR, AFib type (No AFib, persistent/permanent AFib, paroxysmal AFib), DM, and LVEF.

The association between the change of lung fluid volume from baseline at 6 and 12 weeks and novel heart failure biomarkers, including Uric Acid, myeloperoxidase level (MPO), Fibrosis (galectin-3 and soluble ST-2), Myocyte necrosis (hs-cTnT), and Inflammation (hsCRP and interleukin-6), will be assessed similarly.

Sensitivity analyses will be conducted additionally adjusting for AFib type (No AFib, persistent/permanent AFib, paroxysmal AFib) and baseline LVEF. Additional analyses may be performed as appropriate following evaluation of the Sensivest data.

5.5.3 Biomarker Substudy:

- Oxidative stress: Uric Acid
- Fibrosis: galectin-3 (Gal3) and ST-2
- Myocyte necrosis: High sensitivity cardiac troponin T (hs-cTnT)

- Inflammation: high-sensitivity C reactive protein (hsCRP) and interleukin-6 (II-6)
- Advanced glycation end-products: soluble Receptor for Advanced Glycation End Products(sRAGE) and N(6)-Carboxymethyllysine (CML).

Mean, standard deviation, median, and interquartile range (IQR) will be reported for the biomarkers listed above and for their changes from baseline at 6- and 12-week follow-up, for the entire cohort and by treatment group.

The effect of dapagliflozin on the biomarkers at 6- and 12-week will be analyzed in a manner analogous to that of the first primary outcome, although appropriate distributions and link functions will be chosen for the given outcomes.

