The relationship between biomarkers and clinical outcomes, including heart failure specific biomarkers (BNP, NT pro-BNP), as well as patients' symptoms and functional status (KCCQ overall summary score and 6-minute walk test), will be examined using generalized mixed linear models with clinical outcomes as dependent variables (separate models). Independent variables will include the changes from baseline at 6- and 12-week in the aforementioned biomarkers and other potential covariates (age, eGFR, AFib type, DM, and LVEF). The biomarkers will be included in separate models one at a time. Center and patient will be included as random factors. The appropriate distributions and link functions will be chosen for the given outcomes

Additional analyses maybe performed as appropriate following evaluation of the biomarker data.

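### Protocol Appendix C picks biomarkers for the outcome models by their association with the same outcomes, which inflates the reported slopes and conflicts with SAP 5.5.3

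*Protocol*

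**What the plan says.** Protocol Appendix C, Specific Aim #2 plans linear regressions with BNP, NT-proBNP, KCCQ and 6-minute walk as outcomes in separate models. The biomarkers that enter are "chosen based on the strongest univariable relationships between biomarkers and the clinical outcomes". No threshold, number to keep, validation sample or correction is given, and potential confounders are mentioned but not named. The running text of Appendix C (Aim #1) names six biomarkers: uric acid, galectin-3, ST-2, hs-cTnT, hsCRP and IL-6. The Appendix C summary table and Protocol Tables 1 and 3 add CML and sRAGE, which makes eight.

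SAP 5.5.3 lists all eight and says: "The biomarkers will be included in separate models one at a time". It uses generalized mixed linear models, takes biomarker changes from baseline at 6 and 12 weeks as predictors, names the covariates (age, eGFR, AFib type, DM, LVEF) and adds centre and patient as random factors. It has no univariable step. It also allows further analyses once the biomarker data have been seen.

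On error control, SAP 2.5 says: "No adjustments for multiplicity will be made for secondary and exploratory endpoints". Substudy endpoints stand under their own heading in SAP 2.4, and 2.5 does not mention them.

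**The concern.** Under the protocol rule, a biomarker is chosen because its estimated association with an outcome is large in this sample, and the same sample is then used to estimate that association. The estimate carries the favourable chance error that got it chosen. The usual interval and P value ignore the choice. A reader who sees only the chosen biomarkers cannot tell how many were tried.

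The two documents also differ on screening, model, predictors and, within the protocol itself, the candidate list. Neither says which procedure governs, so an analyst could follow either one and claim to be on plan. At stake are the mechanistic statements that could come out of Aim #2. Appendix C predicts that the patients who benefit most will be those whose inflammatory, fibrotic and oxidative-stress markers fall.

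**Working it through.** The documents give no power, error rate or sample size for these models, so there is no figure of the plan's own to reproduce.

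**Inputs from the documents**
- Outcomes: 4 (Appendix C, Aim #2).
- Candidates: m = 6 (Appendix C text) or m = 8 (SAP 5.5.3).
- Level: two-sided 0.05 (Protocol 12.2).
- Patients: all are sampled (Protocol section 14). 2 × 110 = 220 (SAP 1.3), or 250 × (1 − 0.13) = 217.5, about 218 (Protocol 12.3).

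**Assumptions, not in the documents**
- Pairwise correlation among biomarkers: 0 to 0.7.
- True biomarker-outcome correlation r: 0 to 0.30.
- One biomarker kept per outcome.

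**1. Chance that the strongest biomarker reaches P<0.05 when none is related.** For independent biomarkers this is 1 − 0.95^m.
- m = 6: 1 − 0.95^6 = 26.5%.
- m = 8: 1 − 0.95^8 = 33.7%.
- Over four outcomes treated as independent: 1 − 0.95^24 = 70.8% and 1 − 0.95^32 = 80.6%.

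Simulation (6,000 runs, N = 220) with correlated biomarkers gives, per outcome:

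| Pairwise correlation | m = 6 | m = 8 |
|---|---|---|
| 0.3 | 24% | 30% |
| 0.5 | 20% | 25% |
| 0.7 | 17% | 19% |

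N = 110 gives nearly the same rates.

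**2. What that rate measures.** The strongest of m has P<0.05 exactly when at least one of m has P<0.05. Fitting all m one at a time without adjustment has the same rate, with 24 × 0.05 = 1.2 or 32 × 0.05 = 1.6 expected false positives if all are null. Step 1 is therefore a multiplicity figure that both documents share.

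**3. What selection alone adds.** With no true association and N = 218, a biomarker fixed in advance has expected absolute standardised slope 0.798/√218 = 0.054. The strongest of eight averages 0.10 to 0.12 over the assumed correlations (3,000 runs per setting, five adjustment covariates). That is 0.10/0.054 = 1.9 to 0.12/0.054 = 2.2 times as large.

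**4. One biomarker truly related, the rest null and independent (N = 220).** The columns describe the chosen biomarkers that also reached P<0.05.

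| True r | Mean reported absolute r | Share that are null biomarkers, m = 6 / m = 8 |
|---|---|---|
| 0.10 | 0.17 | 39% / 47% |
| 0.15 | 0.19 | 17% / 23% |
| 0.20 | 0.215 | 6% / 10% |
| 0.30 | 0.30 | 0.5% / 0.7% |

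These means carry the significance filter as well as the selection. At N = 220 an absolute r must exceed 1.971/√(218 + 1.971²) = 0.132 to reach P<0.05, so any significant estimate of a true 0.10 is too large. Step 3 has no such filter and isolates the selection effect.

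**The case against.** The best defence is that the SAP already drops the screen. SAP 5.5.3 models the listed biomarkers one at a time with named covariates. The SAP also changes protocol methods elsewhere without announcing it: the Mantel-Haenszel test for the second primary endpoint becomes a logistic model. If the SAP is followed, no association is selected this way. That stands, and it limits the point. It does not settle which text governs, and the SAP's allowance for further analyses leaves room for the protocol rule to return.

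The 26.5% to 33.7% rate also does not show that the protocol rule is worse than the SAP's. This stands in full (step 2).

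The biomarker work is labelled exploratory (Protocol section 14, SAP 1.4), and Aim #2 only examines relationships; the randomised comparison of biomarkers is Aim #1, which has no selection rule. That label can excuse the absence of multiplicity control. It does not make an interval valid after selection on the same outcome.

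A reader might go further and infer that the reported associations would be mostly selection effects, presented as if pre-specified. The documents support neither. In step 4, null biomarkers were a minority of the significant picks in every setting with one true association of 0.10 or more, and the Appendix C table describes several of these markers as already linked to heart-failure severity or prognosis. Appendix C states no test or reporting rule for Aim #2, so how the results would be presented is not known.

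**Conclusion.** The concern holds in a limited form. The protocol's selection rule biases the chosen slopes upward, makes their nominal intervals and P values invalid, and hides how many biomarkers were tried. It also conflicts with SAP 5.5.3, and nothing says which applies.

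The size depends on the true associations, which the documents do not give. Selection alone roughly doubles the expected absolute slope when there is no association. When the true correlation is 0.10, estimates that are both selected and significant average about 0.17; by 0.30 the distortion has gone. These figures rest on the assumed correlations and on one biomarker being kept per outcome. The effect is confined to an exploratory substudy aim and leaves the primary and secondary endpoints, the trial's sample size and safety untouched.

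**What to change.** In Protocol Appendix C, Aim #2, delete the clause that chooses biomarkers by their strongest univariable relationships. Bring its biomarker list and model into line with SAP 5.5.3, including CML and sRAGE.

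In SAP 5.5.3, state that it replaces the Appendix C method. State also that all eight biomarkers are fitted for all four outcomes whatever their univariable association, and that all 8 × 4 = 32 estimates are reported with confidence intervals and labelled exploratory. False-discovery-rate adjusted P values across the 32 may be shown beside the raw ones; in an exploratory substudy this is optional.

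The cost is wording in two documents, a longer table, and fewer associations that can be highlighted. No data collection or study procedure changes.

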Appendix C Biomarker Summary Table:

Circulating biomarkers	Background, rationale, and measurement
Inflammatory	• Several proinflammatory cytokines such as C-reactive protein (CRP), interleukine-6 (IL-6) seem to play a role in the low-grade systemic inflammation observed in diabetics.
(IL-6, HS-CRP)	 HS-CRP is increased in heart failure. Higher levels are associated with features of more severe heart failure and are independently associated with mortality and morbiditys¹⁰
Advanced glycation end-products	 AGEs (circulating carboxymethyl-lysine [CML] and soluble receptor for AGEs [sRAGE]) are products of nonenzymatic glycation and oxidation which are known to rapidly accumulate in vessel walls of diabetics.¹¹
(AGEs) (CML, sRAGE)	• In Mouse RAGE mediates inflammatory signaling, is involved in diabetic macro and microvascular complications, and is associated with increased muscle, cartilage, and vascular stiffness. ¹²⁻¹⁴ Given the adverse effects of AGEs in diabetes, AGEs may play a particularly important role in the pathobiology of heart failure in diabetics
Stress/Fibrosis (Gal-3, soluble ST2)	• Galectin 3 is a biomarker that is actively involved in both inflammatory and fibrotic pathways of cardiac remodeling. Elevated levels of galectin-3 have been found to be significantly associated with higher risk of death in both acute decompensated heart failure and chronic heart failure populations. ¹⁹
	• Soluble ST2 signals the presence and severity of adverse cardiac remodeling and fibrosis. Its levels are elevated in both diabetics and heart failure with reduce ejection fraction, and prognostic of morbidity and mortality. ¹⁸
Oxidative Stress (Uric Acid)	 In Mouse models SGLT-2 have shown to decrease oxidative stress. This is perhaps confirmed as many trials of SGLT-2 have demonstrated a decrease in uric acid.²¹ It is unclear whether the decrease in Uric Acid is through renal loss or truly by a decrease in oxidative stress.
Myocardial Necrosis: (High sensitivity cardiac troponin T (hs-cTnT)	• High-sensitivity troponin assays represent an important advance with added sensitivity for cardiac myocyte necrosis, therefore allowing risk stratification and prognostic information in stable disease states such as chronic systolic heart failure. 23, 24

References:

1. Kannel WB and McGee DL. Diabetes and cardiovascular disease. The Framingham study. *JAMA*. 1979;241:2035-8.

22 APPENDIX D: ARRHYTHMIA SUBSTUDY

Heart Failure (HF) is associated with significant morbidity and mortality, with overall 60-day mortality among clinical trial patients hospitalized for CHF estimated as high as 10 percent.¹ It has been demonstrated that patients with NYHA class I–III tend to die suddenly whereas the death is usually due to refractory failure in those with Class IV symptomatology.² Estimates from the Framingham study show sudden cardiac death which occurs in 30–50% of patients with heart failure.³

It has been shown that beta-blockade and spironolactone reduce such arrhythmias thereby reducing sudden death and total mortality.^{4, 5} Additionally, both have been shown to decrease premature ventricular complexes (PVCs) and non-sustained ventricular tachycardia (NSVT), which have both been shown to correlate with sudden cardiac death in HF patients.⁶

The recently released EMPA-REG OUTCOME trial noted a 38% relative risk reduction of cardiovascular death with empagliflozin, a SGLT-2 inhibitor, versus placebo in patients with diabetes and established CVD.⁷ Though the trial was predominantly of diabetic patients with coronary artery disease (an overall low risk population for arrhythmia and sudden cardiac death compared to HF patients), empagliflozin demonstrated a 31% relative risk reduction of sudden cardiac death compared to placebo.

Atrial arrhythmias are also associated with significant morbidity and mortality amongst patients with HF.⁸ Numerous animal models and some small series of humans demonstrated a potential benefit of thiazolidinedione (TZD) in reducing atrial fibrillation amongst diabetic patients.^{9, 10} It was theorized that this was through a pleiotropic effect perhaps secondary to anti-inflammatory and antioxidant effects of TZDs.¹¹ While the mechanism of benefit of SGLT-2 on cardiovascular outcomes is unknown taking into consideration the aforementioned improvement in cardiac death, sudden cardiac death, death due to worsening HF, and HF hospitalization it could be speculated that this is also likely secondary to pleiotropic effects. It is therefore that we hypothesize dapagliflozin might exert beneficial effects on atrial remodeling reducing AF burden among patients with HF (with and without type 2 diabetes).

Arrhythmia sub study design:

At screening visit (-2 weeks) those likely to be enrolled will be given the option to participate in the arrhythmia sub study. If they elect to enroll they will wear a CARDIOKEY holter monitor for 14 days to establish a baseline. The 14-day holter will be repeated at the 6-week visit to compare change in arrhythmia burden.

When a patient has completed wearing the monitor for 14 days they will send the monitor in a pre paid package to Cardionet for processing. The coordinating center (**Section 2019**) will have a portal with data from all study locations underneath it for data processing and interpretation. Each site will be assigned the necessary number of CARDIOKEY devices, and replacement units ship automatically when a unit is enrolled with a patient. These are shipped second-day air via UPS, so we can set it up so there are enough inventories at each site.

Outcomes of sustained VT episodes, non-sustained VT (NSVT) episodes, VF episodes, atrial fibrillation, PVCs and PACs will be compared between dapagliflozin and placebo (see representative table).

Power Calculation for decrease in PVCs/hour.

Ramires et al reported a baseline PVC/hour burden of 65 ± 15 , this amongst a cohort of NYHA class III patients. After 16 weeks of spironolactone the PVC/hour burden decreased to 17 ± 9 . Given that the patient population of DEFINE-HF population will be less "sick" (NYHA class II and III), we are predicting a baseline PVC burden of 50 ± 15 per hour. Assuming a 14% reduction in PVC per hour after 6 weeks of dapagliflozin; 98 patients would be required in each cohort to achieve 90% power (see Appendix D Table 1).

SensiVest utilizes remote dielectric sensing ReDS[™] technology, to estimate lung fluid volumes. The technology has been adapted from the military who used it to see inside buildings and to find survivors among rubble. Sensible Medical has adapted the same principles and created a vest that when worn sends low-power electromagnetic energy through the lungs, which decipher air content from fluid.¹ Two sensors are attached to the body: one anteriorly on the chest and the other on the back of the patient. Each sensor both transmits and receives the energy either reflected from or transferred through the pulmonary tissue. The signal received reflects the dielectric properties of the section of the lung between the sensors. Water has a very high dielectric coefficient while air in contrast has the lowest dielectric coefficient. These physical properties make pulmonary tissue ideal to sensitively quantify the ratio of fluid to air (or in the case of heart failure estimate volume status and pulmonary edema).²

The device has received both FDA 510k clearance and European CE markings for non-invasive lung fluid monitoring. The waves emitted are low frequency, which do not interfere with any other implantable devices.¹

The accuracy of ReDS was first established using CT as a gold standard and correlating changes in ReDS values among porcine models of heart failure undergoing both fluid challenge and then diuresis. At selected DEFINE-HF study sites patients lung/fluid volume will be measured at randomization (0 weeks), 6, 12 and 13 week visits at rest. The overarching hypothesis is that those on dapagliflozin will have a significantly lower percentage of fluid in their lungs than those on placebo.

Additionally in an attempt to gather more data and correlate lung fluid volumes with heart failure specific quality of life, and biomarkers of fibrosis and remodeling some patients with NYHA class III heart failure at select sites may be able to take a SensiVest home and transmit twice daily lung fluid volumes between randomization and week 13. Patients enrolled prior to SensiVest being available at the trial site will not have any Sensivest measurements preformed. A number of exploratory endpoints will be assessed with this data:

Specific Aim #1: To assess the impact of dapagliflozin vs. placebo on lung fluid volumes in patients with Heart Failure with reduced systolic function.

